# 5.1.12. Subgroup analyses

Summary statistics by visit for the endpoints of HFMSE, RULM and number of new WHO milestones will be presented by age category and by region. It is not planned to do ANCOVA analysis due to the small patient numbers.

# 5.2. Comparisons to external data

The following table summarizes the endpoints, group compared, timepoint and analysis method where additional supplementary comparisons to the DEVOTE higher dose group will be performed:

Study: 232SM203

Statistical Analysis Plan Version: 1.0

Time points	Matched group compared	Analysis
Plasma NfL		
Plasma NfL at Month 6	PS matched CS4 Sham	MI +ANCOVA [Age at first dose, Baseline Plasma NfL, Baseline HFMSE]
	PS matched nusinersen - CS4 only	MI +ANCOVA [Age at first dose, Baseline Plasma NfL, Baseline HFMSE]
HFMSE		
Change to Month 9 [Repeated for Month 6]	PS matched CS4 Sham	MI +ANCOVA [Age at first dose, Baseline Plasma NfL, Baseline HFMSE]
Change to Month 9	PS matched nusinersen – CS4+CS11	MI +ANCOVA [Age at first dose, Baseline HFMSE]
Change to Month 9 [Repeated for Month 6]	PS matched nusinersen – CS4 only	MI +ANCOVA [Age at first dose, Baseline Plasma N-FL, Baseline HFMSE]
Change to Month 9	PS with caliper matched nusinersen A (Clinical trials and PMS)	MI +ANCOVA [Age at first dose, Baseline HFMSE]
Change to Month 9	PS with caliper matched nusinersen B (Clinical trials)	MI +ANCOVA [Age at first dose, Baseline HFMSE]
Change to Month 9 [Repeated for Month 6]	PS with caliper matched CS4 Sham	MI +ANCOVA [Age at first dose, Baseline Plasma NfL, Baseline HFMSE]
Proportion of subjects achieving: >=3 point improvement from baseline at Month 9[Repeated for Month 6]	PS matched CS4 Sham	MI + logistic regression [Age at first dose, Baseline Plasma NfL, Baseline HFMSE]
Proportion of subjects achieving: >=3 point improvement from baseline at Month 9	PS matched nusinersen – CS4+CS11	MI + logistic regression [Age at first dose, Baseline HFMSE]
Proportion of subjects	PS matched	MI + logistic regression [Age at first dose,

#### Study: 232SM203

Statistical Analysis Plan Version: 1.0

Time points	Matched group compared	Analysis
achieving: >=3 point improvement from baseline at Month 9[Repeated for Month 6]	nusinersen – CS4 only	Baseline Plasma NfL and Baseline HFMSE]
Proportion of subjects achieving: >=3 point improvement from baseline at Month 9	PS with caliper matched nusinersen A (Clinical trials and PMS)	MI + logistic regression [Age at first dose, Baseline HFMSE]
Proportion of subjects achieving: >=3 point improvement from baseline at Month 9	PS with caliper matched nusinersen B (Clinical trials)	MI + logistic regression [Age at first dose, Baseline HFMSE]
Proportion of subjects achieving: >=3 point improvement from baseline at Month 9[Repeated for Month 6]	PS with caliper matched CS4 Sham	MI + logistic regression [Age at first dose, Baseline Plasma NfL, Baseline HFMSE]
RULM		
Change to Month 9 [Repeated for Month 6]	PS matched CS4 Sham	MI +ANCOVA [Age at first dose, Baseline Plasma NfL, Baseline RULM]
Change to Month 9	PS matched nusinersen – CS4+CS11	MI +ANCOVA [Age at first dose, Baseline RULM]
Change to Month 9 [Repeated for Month 6]	PS matched nusinersen – CS4 only	MI +ANCOVA [Age at first dose, Baseline Plasma NfL, Baseline RULM]
Change to Month 9	PS with caliper matched nusinersen B (Clinical trials)	MI +ANCOVA [Age at first dose, Baseline RULM]
Change to Month 9 [Repeated for Month 6]	PS with caliper matched CS4 Sham	MI +ANCOVA [Age at first dose, Baseline Plasma NfL, Baseline RULM]

Total number of new WHO motor milestones

Study: 232SM203

Statistical Analysis Plan Version: 1.0

Time points	Matched group compared	Analysis
Change to Month 9 [Repeated for Month 6]	PS matched CS4 Sham	ANCOVA [Age at first dose, Baseline plasma NfL, Baseline number of WHO milestones]
Change to Month 9	PS matched nusinersen – CS4+CS11	ANCOVA [Age at first dose, Baseline number of WHO milestones]
Change to Month 9 [Repeated for Month 6]	PS matched nusinersen – CS4 only	ANCOVA [Age at first dose, Baseline plasma NfL, Baseline number of WHO milestones
Change to Month 9	PS with caliper matched nusinersen B (Clinical trials)	ANCOVA [Age at first dose, Baseline number of WHO milestones]
Change to Month 9 [Repeated for Month 6]	PS with caliper matched CS4 Sham	ANCOVA [Age at first dose, Baseline number of WHO milestones]

Square brackets in the 3rd column denotes the covariates to include in the ANCOVA/Logistic regression model. If analysis is also using multiple imputation, then these covariates will be included in the imputation step.

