#### 2. Higher dose versus 12 mg nusinersen from CS4 and CS11 controlled clinical trials L3M6 dosing regimen.

The matching design will be the same design as the design for comparison 2 but will use a smaller pool of patients as Japan PMS patients will not be included. In this analysis, baseline RULM will also be included as a covariate for matching

3. Matching design for comparison 4: higher dose versus CS4 Sham control

The matching design will be as shown in the table below. In this analysis baseline RULM will also be included as a covariate for matching

Design	232SM203 higher dose	CS4 Sham
1) Match 1 to 2	N= 16	N= 32
2) Match 1 to 1	N= 16	N= 16

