#### Main Analysis

The main analysis is to compare the total number of new motor milestones achieved at Day 302 between 50/28 mg Group and 12/12 mg Group, based on the ITT set. Missing data will be handled as described above and a total score for each visit calculated by summing the six milestones.

For each milestone the Day 302 and baseline values will be compared and if the subject can achieve a new milestone compared to baseline, then it will be counted +1, if the subject is unable to achieve the milestone, then it will be scored -1 and if the milestone has been maintained then it will be scored 0. These scores will then be summed to give a total score which could range between -6 (if a subject was able to perform all milestones at baseline but lost the ability and could not perform any milestones at Day 302) and +6 (if a subject was unable to achieve any milestones at baseline but could achieve all at Day 302).

The total number of new milestones achieved by each subject at Day 302 will be compared between treatment groups by ANCOVA with treatment group as the factor and subject age at screening, baseline Plasma NfL, and baseline number of milestones as covariates.

The following sensitivity analyses will be performed:

Product: Nusinersen	Statistical Analysis Plan
Study: 232SM203	Version: 1.0

- The main analysis will be repeated using the PPS.
- The analysis will be repeated in the ITT, with an exception to assign the worst of last available observation and zero (0) new motor milestones achieved for subjects who terminate the study prior to the Day 302 assessment.

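### Part B later-onset SAP, section 5.2: the WHO milestone model for the caliper-matched CS4 sham group omits baseline plasma NfL, which every other CS4-only model includes, and no reason is given

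*SAP*

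**What the plan says.** Section 5.2 lists the supplementary comparisons of the higher-dose group with matched external groups. A note under the table says that the square brackets state the covariate set: the bracketed list "denotes the covariates to include in the ANCOVA/Logistic regression model". The brackets are therefore model instructions.

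For total number of new WHO motor milestones, two rows use CS4 sham controls:

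- PS-matched CS4 sham: "ANCOVA [Age at first dose, Baseline plasma NfL, Baseline number of WHO milestones".
- Caliper-matched CS4 sham (last row of the table): "ANCOVA [Age at first dose, Baseline number of WHO milestones".

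For the other endpoints, both the PS-matched and the caliper-matched CS4 sham rows include NfL:

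- HFMSE change: "MI +ANCOVA [Age at first dose, Baseline Plasma NfL, Baseline HFMSE".
- HFMSE responders (3 points or more): "MI + logistic regression [Age at first dose, Baseline Plasma NfL, Baseline HFMSE".
- RULM: "MI +ANCOVA [Age at first dose, Baseline Plasma NfL, Baseline RULM".

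Within the study, the main analysis of new WHO milestones takes age at screening, "baseline Plasma NfL, and baseline number of milestones as covariates".

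Section 2.4.5 calls the external comparisons supportive, and section 5.2 calls them supplementary.

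**The concern.** The external comparisons are not randomised, so the covariate list carries part of the protection against imbalance. The table otherwise follows one rule: NfL is in the model when the controls come from CS4 alone, and out when the pool includes CS11 or the Japan PMS study. The last row breaks that rule. Its covariate list is the same as in the row directly above it (caliper-matched nusinersen B, which pools CS4 and CS11), so it looks like a drafting slip.

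Two things are at stake. If matching leaves the groups unequal on NfL, this model does not correct for it. And the two WHO sham models differ both in how the controls were chosen and in the covariates used. For HFMSE and RULM the two corresponding sham models have the same covariates.

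**Working it through.** The plan gives no power, alpha or sample-size figure on this point, so there is none to reproduce. The check is a count of the table rows, followed by an illustration of possible size.

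**1. Count of the model rows in section 5.2**

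| Endpoint | CS4 sham: with NfL / rows | CS4-only nusinersen: with NfL / rows | Pool with CS11 or PMS: with NfL / rows |
|---|---|---|---|
| Plasma NfL | 1 / 1 | 1 / 1 | – |
| HFMSE change | 2 / 2 | 1 / 1 | 0 / 3 |
| HFMSE responders | 2 / 2 | 1 / 1 | 0 / 3 |
| RULM | 2 / 2 | 1 / 1 | 0 / 2 |
| WHO milestones | 1 / 2 | 1 / 1 | 0 / 2 |
| Total | 8 / 9 | 5 / 5 | 0 / 10 |

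Rows: 9 + 5 + 10 = 24. CS4-only comparators: 8 + 5 = 13 of 9 + 5 = 14 with NfL. In the two plasma NfL rows, baseline NfL is the endpoint's own baseline. Without them the count is 11 of 12, and the same single row is the exception.

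**2. Reasons that might explain the row**

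- *NfL not measured in this matched set.* The same caliper-matched sham set is adjusted for NfL for HFMSE change, HFMSE responders and RULM.
- *NfL not thought relevant to milestones.* The within-study WHO analysis, the PS-matched sham WHO row and the CS4-only nusinersen WHO row all include it.
- *No multiple imputation for WHO, so children without NfL would be lost.* The PS-matched sham WHO row has no multiple imputation either, and it keeps NfL.

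None of these separates the last row from its PS-matched counterpart.

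**3. Possible size (illustration)**

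The documents give neither the NfL–milestone relation nor the imbalance after matching. Both are assumed here: a standardised NfL coefficient b of 0.2 to 0.5, and a residual NfL imbalance d of 0 to 0.5 SD. Group sizes follow the CS4 sham matching design: 16 higher-dose children against 16 or 32 sham children. That the caliper-matched set has these sizes is also an assumption.

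Bias in outcome SD units = b × d. Standard error in the same units, ignoring any variance explained by covariates = √(1/16 + 1/n), where n is the number of sham children.

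- Lower end: b × 0 = 0 for any b.
- Upper end: 0.5 × 0.5 = 0.25 SD.
- 16 v 16: SE = √(1/16 + 1/16) = 0.354; 0.25 / 0.354 = 0.71 SE.
- 16 v 32: SE = √(1/16 + 1/32) = 0.306; 0.25 / 0.306 = 0.82 SE.
- Middle case, b = 0.2 and d = 0.25: 0.05 SD, or 0.14 SE (16 v 16) and 0.16 SE (16 v 32).

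**4. Cost in degrees of freedom**

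The current model has four parameters (intercept, treatment, age, baseline milestones). Residual degrees of freedom are 32 − 4 = 28 or 48 − 4 = 44. With NfL they become 27 or 43.

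**The case against.** The strongest objection is that the groups are matched before the model is fitted. The full list of matching covariates is not visible in the public text. Section 5.1.2 shows only an addition to it: for the CS4 and CS11 design it says "In this analysis, baseline RULM will also be included as a covariate for matching", and it says the same for the CS4 sham design. If NfL is on the list, the missing term may leave little or no bias. This stands. A reader might infer that the caliper result is confounded by NfL, but the documents do not show that.

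A reader might also infer that the two WHO sham results cannot be compared at all. That goes too far. They can be set side by side; what is lost is attribution of a difference to the matching. Even that would not be fully clean after the fix, because section 5.1.2 allows 1:2 or 1:1 matching and lets the independent statistician use another algorithm if the planned one fails. Nor does the SAP say that the caliper set is a check on the PS-matched set. That role is inferred from the parallel rows.

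On availability, the other caliper-matched sham rows use multiple imputation with these covariates in the imputation step, so they do not prove that NfL is complete for every child. This stands as a caution about the fix. It does not explain the row, since the PS-matched WHO row accepts the same risk.

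Finally, the same covariate string appears in the CS4+CS11 and caliper-matched nusinersen B rows for WHO milestones. There it fits the table's rule and is not in question.

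**Conclusion.** The point holds for the last row only, at Month 9 and its Month 6 repeat. That model is the sole exception among 14 CS4-only models, and the SAP gives no reason for it. It adjusts for less than the SAP's own covariate set, so any NfL imbalance left by matching would stay in the estimate. A difference from the PS-matched sham WHO result would mix matching with covariate choice.

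The size is small and uncertain: 0 to 0.25 outcome SD, or at most about 0.7 to 0.8 of a standard error. This rests on an assumed NfL coefficient, an assumed residual imbalance and assumed group sizes. It is zero if matching balances NfL. The comparison is supplementary, in a population with no primary efficacy endpoint and a sample size not set on statistical grounds. No confirmatory conclusion is affected. It is an inexpensive improvement, worth making because the plan already uses this covariate for the same matched set and for the same endpoint elsewhere.

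**What to change.** In the last row of the section 5.2 table, replace the model by the one already used for the PS-matched CS4 sham WHO row: "ANCOVA [Age at first dose, Baseline plasma NfL, Baseline number of WHO milestones". Leave the CS4+CS11 and caliper-matched nusinersen B rows as they are. All 9 CS4-sham models and all 14 CS4-only models would then include NfL. If the omission was intended, state the reason under the table instead.

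The cost is one table cell and one degree of freedom. Because the WHO rows do not use multiple imputation, a child without a baseline NfL value would drop out of this model. The plan already accepts that in the PS-matched row; reporting the number of children in each model would make any loss visible.

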# 6. Safety Endpoints

The analysis of safety will be performed using the Safety Set. The main analysis will be to compare the two arms of 232SM203. Presentations will also be included for AEs, SAEs and related AEs comparing sham from the matched CS4 Sham to the 232SM203 higher dose arm.

AEs will be analyzed based on the principle of treatment emergence where treatment emergence will be relative to the first dose of nusinersen. An AE will be regarded as treatment-emergent if it was present prior to receiving the first dose of nusinersen and subsequently worsened in severity or was not present prior to receiving the first dose of nusinersen but subsequently appear. Refer to Appendix A for more details about AE with missing start or stop dates.

A participant having the same AE preferred term more than once will be counted only once in the incidence for that event. Multiple occurrences of the same adverse event for the same subject will all be counted in the frequency for that adverse event.

Product: Nusinersen	Statistical Analysis Plan
Study: 232SM203	Version: 1.0

The occurrence of the AE with the greatest severity will be used in the calculation of incidence by severity. The AE relationship to treatment or LP/sham procedure is captured as related or not related. In the event the relationship is missing then this will be considered related.

Due to the long half-life of nusinersen, analyses of treatment-emergent adverse events will include all events reported during the study. Adverse Events will be coded using the Medical Dictionary for Regulatory Activities.

The following presentations will be shown:

- an overall summary showing, for each treatment group, the number and percentage of subjects with an adverse event, a mild, moderate or severe event, an event related to study drug, an event related to lumbar puncture /sham procedure, a serious event, a serious event related to study drug, an event leading to study drug withdrawal, an event leading to study withdrawal, and a fatal event.
- incidence and frequency by system organ class and preferred term
- incidence and frequency by preferred term
- incidence and frequency, by preferred term, in at least 2 subjects in any treatment group
- incidence of adverse events by maximum severity by preferred term
- incidence and frequency of severe events by system organ class and preferred term
- incidence and frequency of events related to study drug by system organ class and preferred term
- incidence and frequency of events related to lumbar puncture /sham procedure (as assessed by the investigator) by system organ class and preferred term
- incidence by system organ class and preferred term that occurred within 24 hours of Dosing or Sham Procedure
- incidence by system organ class and preferred term that occurred within 72 hours of Dosing or Sham Procedure
- incidence and frequency of serious adverse events by system organ class and preferred term
- incidence and frequency of serious adverse events related to study drug by system organ class and preferred term
- incidence of events that led to fatal outcome
- incidence of events leading to study drug withdrawal by system organ class and preferred term

- incidence of events leading to withdrawal from study by system organ class and preferred term
- incidence and frequency of adverse events over time by system organ class and preferred term.
- incidence and frequency of adverse events antibody status by system organ class and preferred term.

A separate table will also be presented to show an overall summary of COVID-19 pandemic related AEs.

Listings of the following events will be produced.

- AEs
- SAEs
- AE with fatal outcome
- AEs led to study drug withdrawal
- AEs led to withdrawal from study
- AEs related to lumbar puncture/sham procedure
- AEs related to study drug

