## 3.2. Study Treatments

The main presentations of data will use the following groups:

Baseline characteristics displays for assessing sham and 232SM203 similarity.

(	CS3B	CS3B	2.	32SM203	
Shan	n control	rol Matched Sham control		50/28 mg nusinersen	Total
Baseline character	ristics, dispositio	n, exposure, time o	n study		
Matched CS3	В	232SM	203		
Matched CS3	B			Total	

Product: Nusinersen
Study: 232SM203

For summaries of post-baseline efficacy by visit/time

Matched CS3B	232SM203	
	12/12 mg	50/28 mg
Sham control	nusinersen	nusinersen

Primary and secondary endpoints analyses comparing sham and key adverse event displays

Matched CS3B	232SM203
_	50/28 mg
Sham control	nusinersen

For secondary endpoints comparing higher dose to 12/12 mg in 232SM203, safety and post baseline safety parameters:

	232SM203
12/12 mg	50/28 mg
nusinersen	nusinersen

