## Sensitivity analyses

- o Repeated using CS3B sham Day 183 matched to 232SM203 efficacy set (sensitivity)
- Repeated using Greedy matched set (sensitivity)
- Adjustment of ranking criteria for JRT for withdrawals not due to death In order to test the sensitivity of handling withdrawals not due to death, ranking criteria will be adjusted as a sensitivity analysis for JRT These analyses will be performed as described in Section 6.1
- Adjustment of ranking criteria for JRT for permanent ventilation
- Main analysis will be repeated using an ANCOVA model where the variance in each treatment group is estimated separately

In order to examine the impact of considering permanent ventilation in evaluation of this endpoint the ranking criteria will be adjusted as sensitivity analysis for JRT. These analyses will be performed as described in Section 6.1.

• Exclusion of deaths from MI model

The MI model will be run for CHOP INTEND total score for the ITT population excluding data from any subjects who died prior to Day 183, so that missing data for survivors are not influenced by any systematic difference there may be in data from subjects who died. The joint rank analysis will then be conducted using these imputed datasets for survivors and deaths will be ranked the lowest based on time of death. The pvalue from the joint rank analysis with MI will be presented as per the main analysis.

• Data truncated to include only up to and including Day 183

Product: Nusinersen	Statistical Analysis Plan
Study: 232SM203	Version: 3.0 Final

In the event that a participant has CHOP INTEND missing items at Day 183 then data from later visits is utilized as part of interpolation. Some of the subjects in the CS3B study only have data up to Day 183 before the study was stopped in contrast to 232SM203 where all subjects potentially could be followed to Day 302. In order to investigate the sensitivity of the analysis to this truncation an additional analysis will be performed where only the data up to and including Day 183 is utilized from both CS3B and 232SM203 and the item level imputation approach described in Section 6.1 is applied.

- The main analysis will be repeated incorporating Jump to reference in the MI step.
- The main analysis will be repeated for the following subgroups:
  - disease duration
  - baseline CHOP INTEND

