### 2.4.1.CS4 Study

CS4 was a phase 3, randomized, double-blind, sham-procedure controlled study to assess the clinical efficacy and safety of nusinersen administered intrathecally in patients with later-onset spinal muscular atrophy. The study had a planned follow-up from first dose of 15 months.

Key eligibility criteria were onset of symptoms of SMA at > 6 months of age, aged between 2 and 12 years and ability to sit but never have achieved the ability to walk independently. The primary endpoint was the change in HFMSE score from baseline to Month 15 and secondary endpoints included the proportion of participants achieving a 3 point improvement on the HFMSE, change in RULM and proportion of participants achieving new WHO motor milestones.

The first patient was dosed in November 2014 and the last patient visit was February 2017. The study was stopped early based on the results of an interim safety and efficacy analysis and the study results were published (Mercuri et al. 2018).

A difference between CS4 and later-onset part B of 232SM203 was that in CS4, patients received 3 loading doses of 12 mg at days 1, 29, and 85 and then a dose at Day 274 in contrast to 232SM203 where 4 loading doses at Days 1, 15, 29 and 64 and then a dose at Day 183 is administered consistent with the nusinersen label in the majority of geographies.

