#### 3.2. Study Treatments

The main presentations of data will be as follows:

Baseline characteristics, disposition, exposure, time on study and adverse event displays

	232SM203	
12/12 mg nusinersen	50/28 mg nusinersen	Total

For baseline summaries including external data, all patients available in the pool will be included in the first column and then the matched patients, in the  $2^{nd}$  column.

|--|

Product: Nusinersen			Statistical Analysis Plan
Study: 232SM203			Version: 1.0
Shar	n	Sham	50/28 mg nusinersen
For efficacy endpoints, s	afety other than AES,		:
For efficacy endpoints, s	afety other than AES,		:
For efficacy endpoints, s		SM203	

For summaries of adverse events and efficacy including external data:

Matched CS4	232SM203
sham	50/28 mg nusinersen

The total study duration for each participant will be approximately 323 to 420 days:

- Screening: 21 days
- Loading period: 64 days
- Maintenance period: 215 days
- Follow-up: 23 to 120 days

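### Part B later-onset SAP: the adverse event displays of matched CS4 sham against 50/28 mg use crude incidence over unequal follow-up, and the planned follow-up adjusted rates only partly cover this

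*SAP*

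**What the plan says.** The Part B later-onset SAP, section 6 (Safety Endpoints), makes the comparison of the two randomised arms the main safety analysis and then adds an external one: "Presentations will also be included for AEs, SAEs and related AEs comparing sham from the matched CS4 Sham to the 232SM203 higher dose arm". Section 3.2 gives it its own two-column layout, matched CS4 sham beside 50/28 mg. Incidence counts a participant once per preferred term, frequency counts every occurrence, and "analyses of treatment-emergent adverse events will include all events reported during the study".

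On duration, section 2.4.1 says of CS4: "The study had a planned follow-up from first dose of 15 months". It also says: "The study was stopped early based on the results of an interim safety and efficacy analysis". It does not report the follow-up achieved. For 232SM203, section 3.2 says: "The total study duration for each participant will be approximately 323 to 420 days". That total includes "Screening: 21 days".

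Further on in section 6, under the heading on follow-up adjusted incidence, two rate tables are planned by study group, system organ class and preferred term. One divides participants with an event by total follow-up; the other divides the number of events by total follow-up. Section 7.1.1 of the infantile-onset SAP plans the same two tables, and section 3.2 of that SAP sets matched CS3B sham beside 50/28 mg for "Primary and secondary endpoints analyses comparing sham and key adverse event displays".

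**The concern.** Crude incidence rises with time under observation. If two studies watch their participants for different lengths of time, equal risks give unequal percentages, and a real difference can be hidden or a false one produced. Both randomised arms receive nusinersen, so matched sham is the only untreated reference for the harms of the higher dose in these displays.

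The SAP handles this for efficacy. Sections 4.4, 5.1.1 and 5.2 tie the external comparisons to Month 6 or Month 9 and to visits that both sources share. No equivalent rule exists for adverse events. Whether the planned rates fill the gap depends on which columns and event types they cover, and the text does not say.

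**Working it through.** **Inputs.** Later-onset SAP section 3.2: screening 21 days, loading 64, maintenance 215, follow-up 23 to 120. Section 2.4.1: CS4 planned for 15 months from first dose. The documents give no adverse event rates, so the incidences below are assumed illustrations.

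**1. The plan's own figure.** 21 + 64 + 215 + 23 = 323 and 21 + 64 + 215 + 120 = 420 days, as stated. Without screening: 323 − 21 = 302 and 420 − 21 = 399 days after first dose.

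**2. Ratio of windows.** 15 × 365.25/12 = 457 days. 457/302 = 1.51 and 457/399 = 1.14.

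**3. Crude incidence at equal risk.** With the same constant hazard in both groups, incidence p over t days on 50/28 mg becomes 1 − (1 − p)^(T/t) over T days in sham. With T = 457:

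| 50/28 mg | Sham, t = 399 | Sham, t = 302 |
|---|---|---|
| 10% | 11.4% | 14.7% |
| 20% | 22.5% | 28.6% |
| 30% | 33.5% | 41.7% |

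**4. Effect of the early stop.** The gap is zero when T = t, that is at 302/30.44 = 9.9 months or 399/30.44 = 13.1 months. Taking mean sham follow-up of 9 to 15 months as an assumed range, 30% on 50/28 mg corresponds in sham to 27.6% to 41.7% (t = 302) or 21.7% to 33.5% (t = 399). The sign therefore depends on a figure that the SAP does not give.

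**5. What the planned rates do under the same model (T = 457).**
- Events over total follow-up: equal in the two groups, sham to 50/28 mg ratio 1.00.
- Participants with an event over total follow-up, p = 30%: for t = 302, 0.333 against 0.363 per year, ratio 0.92; for t = 399, 0.268 against 0.275, ratio 0.98. Time after the first event stays in the denominator, so a small bias remains, opposite in direction to the crude one.

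**6. Coverage.** The sham displays named in section 6 are AEs, SAEs and related AEs. The adjusted tables are described for adverse events by system organ class and preferred term. SAEs, related AEs and the overall summary are not mentioned, and the sham column is not named. The table of adverse events over time does not name it either.

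**The case against.** The strongest reply is that the adjustment is already planned. At equal constant hazard the event-based rate removes the bias. The randomised arms share one schedule, so the cross-study comparison is where such rates matter most, and it is natural to read them as including sham. The subsection that follows deals with how CS4 adverse events are reported, which supports that reading. This stands for adverse events by preferred term, but it has to be inferred, and it does not extend to SAEs, related AEs or the overall summary.

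The effect is also modest. The sham display is supportive and no adverse event test is planned. With 16 on 50/28 mg and 16 or 32 matched sham, the 20% against 28.6% example is 0.086 × 16 = 1.4 children per 16. Its standard error is √(0.2 × 0.8/16 + 0.286 × 0.714/n), or 15 points for n = 16 and 13 for n = 32. That stands.

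Two stronger readings are tempting, and the documents support neither:
- A reader might infer that the higher dose will look safer than it is. That needs achieved sham follow-up longer than in 232SM203, and CS4 stopped early with achieved follow-up not given.
- A reader might infer a measured opposite bias in the infantile part, because CS3B has 37 sham participants in its Day 183 efficacy set and 28 in its Day 302 set, and because "Some of the subjects in the CS3B study only have data up to Day 183 before the study was stopped". Those sets are defined by opportunity to attend an efficacy visit, and the sentence concerns CHOP INTEND data. Neither measures adverse event follow-up. Cutting the infantile display at Day 183 would also drop every event after the Day 279 dose.

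**Conclusion.** The point holds in a limited form. The crude AE, SAE and related-AE contrast of matched CS4 sham with 50/28 mg runs over unequal windows, and the adjusted rates as written repair it only in part. If CS4 sham reached its planned 15 months and hazards are constant and equal, 20% on 50/28 mg would show as 22.5% to 28.6% in sham. The gap closes at about 10 months of sham follow-up (against 302 days) or 13 months (against 399 days) and reverses below that, so neither its size nor its sign can be fixed from the SAP.

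The main safety analysis, 50/28 mg against 12 mg within 232SM203, is not affected. For the infantile SAP, all that remains is to state what its adjusted tables cover.

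**What to change.** - **Later-onset SAP, section 6.** In the matched CS4 sham against 50/28 mg displays of AEs, SAEs and related AEs, count only events with onset up to Day 302 in both groups. Report how many in each group are still followed at Day 302, because sham participants lost before then through the early stop would still have a shorter window.
- **Adjusted rates, later-onset section 6 and infantile section 7.1.1.** State that these tables include the matched sham column, and extend them to SAEs and related AEs. Use events over person-time, or first events over time to first event or censoring, in place of participants over entire follow-up.
- **No change** to the all-events tables for 50/28 mg against 12 mg within 232SM203.

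The cost is a few sentences of SAP text, one onset-date filter and some additional rate tables; no new data are needed. Late events leave the later-onset sham display only and remain in the full tables and listings.
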